7. ADVERSE EVENT MONITORING AND REPORTING

AEs will be recorded and monitored and, when appropriate, reported to SAHPRA and others involved in an investigation (sponsors, IRBs, and investigators) in accordance with existing statutes. In addition, to assist in monitoring safety and making required reports, AEs will be categorized in accordance with the Guidance for Industry: Toxicity Grading Scale for Healthy Adult and Adolescent Volunteers Enrolled in Preventive Vaccine Clinical Trials (2007). These scales are described in more detail in the following sections.

7.1. Guidance for Industry: Toxicity Grading Scale for Healthy Adult and Adolescent Volunteers Enrolled in Preventive Vaccine Clinical Trials (2007)

The enrollment of healthy volunteers warrants a very low tolerance for risk. The Guidance for Industry: Toxicity Grading Scale for Healthy Adult and Adolescent Volunteers Enrolled in Preventive Vaccine Clinical Trials (2007) will be used to assess the severity of clinical and laboratory abnormalities in healthy adult volunteers enrolled in this study. AEs will be graded according to the following tables from The Guidance for Industry: Toxicity Grading Scale for Healthy Adult and Adolescent Volunteers Enrolled in Preventive Vaccine Clinical Trials (2007).

Table 11: Clinical Abnormalities: Local Reaction to Injectable Products

Local Reaction to Injectable Product	Mild (Grade 1)	Moderate (Grade 2)	Severe (Grade 3)	Potentially Life Threatening (Grade 4)
Pain	Does not interfere with activity	Repeated use of non-narcotic pain reliever > 24 hours or interferes with activity	Any use of narcotic pain reliever or prevents daily activity	Emergency room (ER) visit or hospitalization
Tenderness	Mild discomfort to touch	Discomfort with movement	Significant discomfort at rest	ER visit or hospitalization
Erythema/Redness *	2.5 – 5 cm	5.1 – 10 cm	> 10 cm	Necrosis or exfoliative dermatitis
Induration/Swelling **	2.5 – 5 cm and does not interfere with activity	5.1 – 10 cm or interferes with activity	> 10 cm or prevents daily activity	Necrosis

* In addition to grading the measured local reaction at the greatest single diameter, the measurement should be recorded as a continuous variable.

** Induration/Swelling should be evaluated and graded using the functional scale as well as the actual measurement.

Table 12: Clinical Abnormalities: Vital Signs

Vital Signs *	Mild (Grade 1)	Moderate (Grade 2)	Severe (Grade 3)	Potentially Life Threatening (Grade 4)

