APPENDIX 1. SAMPLE DIARY FOR SOLICITED EVENTS

STUDY NUMBER*: _____

Patient Number*		Date of Vaccine Administration	/	/	/	*To be completed by the site		
-----------------	--	--------------------------------	---	---	---	------------------------------	--	--

Please answer all questions below daily for 7 days, beginning with day of treatment. Be sure to bring back this completed diary to your next clinic visit.

Intramuscular: Solicited local AEs	Instructions	Date / /						
1. Is there redness at the injection site?	Check:  Yes or  No If yes, measure longest diameter in cm	 Yes or  No _____ cm	 Yes or  No _____ cm	 Yes or  No _____ cm	 Yes or  No _____ cm	 Yes or  No _____ cm	 Yes or  No _____ cm	 Yes or  No _____ cm
2. Is there firmness at the injection site?	Check:  Yes or  No	 Yes or  No	 Yes or  No	 Yes or  No	 Yes or  No	 Yes or  No	 Yes or  No	 Yes or  No
3. Is there swelling at the injection site?	Check:  Yes or  No If yes, measure longest diameter in cm	 Yes or  No _____ cm	 Yes or  No _____ cm	 Yes or  No _____ cm	 Yes or  No _____ cm	 Yes or  No _____ cm	 Yes or  No _____ cm	 Yes or  No _____ cm

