8. Is there bruising at the injection site?	Check:  Yes or  No	 Yes or  No	 Yes or  No	 Yes or  No	 Yes or  No	 Yes or  No	 Yes or  No	 Yes or  No

Grading Injection Site Pain or Itching:

Mild – Noticeable, does not interfere with activity

Moderate – Interferes with activity, limiting activities of daily life

Severe – Severely limiting self-care activities of daily living, incapacitating

STUDY NUMBER*: _____

Patient Number*		Date of Vaccine Administration	/	/	/	*To be completed by the site		
-----------------	--	--------------------------------	---	---	---	------------------------------	--	--

Please answer all questions below daily for 7 days, beginning with day of treatment. Be sure to bring back this completed diary to your next clinic visit.

| Solicited systemic AEs | Instructions | Date / / |
|---|---|---|---|---|---|---|---|---|
| 1. Have you experienced any chills? | Check:
 Yes or  No
If yes, tell us if the chills are mild, moderate or severe |  Yes or  No
Mild
Moderate
Severe |
| 2. Have you experienced nausea? | Check:
 Yes or  No
If yes, tell us if the nausea is mild, moderate or severe |  Yes or  No
Mild
Moderate
Severe |
| 3. Have you experienced vomiting? | Check:
 Yes or  No
If yes, tell us if the vomiting is mild, moderate or severe |  Yes or  No
Mild
Moderate
Severe |
| 4. Have you experienced diarrhea? | Check:
 Yes or  No
If yes, tell us if the diarrhea is mild, moderate or severe |  Yes or  No
Mild
Moderate
Severe |
| 5. Have you experienced any headache? | Check:
 Yes or  No
If yes, tell us if the headache is mild, moderate or severe |  Yes or  No
Mild
Moderate
Severe |

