 Severe: Significant; any use of narcotic pain reliever or prevents daily activity

Grading Fatigue:

Mild: No interference with activity
 Moderate: Some interference with activity
 Severe: Significant; prevents daily activity

Grading Muscle Pain:

Mild: No interference with activity
 Moderate: Some interference with activity
 Severe: Significant; prevents daily activity

Grading Abdominal Discomfort/Pain:

Mild: No interference with activity
 Moderate: Some interference with activity
 Severe: Significant; prevents daily activity

Grading Joint Pain:

Mild: No interference with activity
 Moderate: Some interference with activity
 Severe: Significant; prevents daily activity

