APPENDIX 2. SAMPLE DIARY FOR UNSOLICITED EVENTS

STUDY NUMBER*: _____

Patient Number*	Date of Vaccine Administration	/ /	*To be completed by the site
-----------------	--------------------------------	-----	------------------------------

Please complete this diary every day beginning on the day you receive the first dose of study vaccine until 30 days after you receive the last dose of study vaccine. Each page has space for recording 7 days of information. You will be provided with enough pages to last until 30 days after you receive the last dose of study vaccine. Be sure to bring this diary each time you visit the clinic and refer to this diary when study personnel contact you by telephone for schedule safety follow up assessments.

Unsolicited AEs	Date / /						

Please describe any unusual feelings of discomfort, signs or symptoms that are not specified on the other daily diaries. If you do not experience these feelings, signs, or symptoms, please mark "no additional symptoms to report". For each separate sign and symptom you report in the diary, please note the following:
 
 • How intense it is, either Mild (no interference with activity), Moderate (some interference with activity), or Severe (significant; prevents daily activity) • How long it lasts • Any actions you took to manage the symptoms (for instance, taking medication) 							

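### The Appendix 1 sample diary does not collect what Table 11 needs to grade injection-site pain, swelling and firmness, so some Grade 3 local reactions could be recorded low

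*Combined protocol and SAP*

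**What the plan says.** **Grading standard.** Section 7.1, Table 11 is the scale for local reactions. Pain is Grade 3 with "Any use of narcotic pain reliever or prevents daily activity". Induration/swelling is Grade 3 at "> 10 cm or prevents daily activity". A footnote adds: "Induration/Swelling should be evaluated and graded using the functional scale as well as the actual measurement".

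**Sample diary (Appendix 1).** Pain and itching share one set of anchors: "Moderate – Interferes with activity, limiting activities of daily life" and "Severe – Severely limiting self-care activities of daily living, incapacitating". Item 3 asks whether there is swelling and takes its longest diameter. Item 2 asks "Is there firmness at the injection site" and takes Yes or No only. Item 5 asks for the names of medications used for pain or itching.

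**The study's other anchors.** For fatigue, muscle, abdominal and joint pain, Appendix 1 uses "Severe: Significant; prevents daily activity". Appendix 2 has "Severe (significant; prevents daily activity" for unsolicited events.

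**Where the grade is used.** Severity of solicited local reactions is a phase 1 primary endpoint (3.4.1.1) and a phase 2 secondary endpoint (3.4.2.2.1). In phase 1, vaccination is suspended when 3 or more participants have the same or similar related Grade 3 event (7.8.2 rule 2). Enrollment into later cohorts is suspended when 3 or more have a related event of Grade 3 or above (7.8.2.1(a)).

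**Who grades.** A qualified investigator evaluates severity on the Guidance scale (7.4, 7.4.1). Solicited events are collected at visits as well as by diary (6.3.1).

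**The concern.** The diary is the only day-by-day record of the 7-day reactogenicity window, and for three local reactions its answers do not map to the protocol's own grades. A participant whose arm hurts too much to work, but who can still wash and dress, meets Table 11 Grade 3 and could reasonably circle Moderate. A small swelling that stops daily activity is Grade 3 by function but looks like Grade 1 by diameter. Firmness alone cannot be graded from the diary at all. The documents give no rule for turning diary answers into Table 11 grades.

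At stake are the reported severity in a primary endpoint and two suspension rules with a threshold of three participants, where one record can decide whether the count is reached.

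**Working it through.** The plan states no figure to reproduce: Section 8.4 says the sample sizes have no statistical basis, and no operating characteristics are given for the rules. The check is a comparison of texts, followed by an illustration on assumed rates.

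**1. Side by side**

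| Reaction | Table 11, Grade 3 | Diary collects | Missing |
|---|---|---|---|
| Pain | Narcotic use, or daily activity prevented | Daily mild/moderate/severe; medication names | An anchor at prevented daily activity |
| Swelling | Over 10 cm, or daily activity prevented | Yes/No; diameter | Function |
| Firmness (induration) | Same row as swelling | Yes/No | Size and function |
| Redness | Over 10 cm | Yes/No; diameter | Nothing |

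Narcotic use and swelling over 10 cm are therefore visible; the gap is the functional criterion, plus size for firmness. For example, a 3 cm swelling lies in the 2.5–5 cm band (Grade 1 by size) but is Grade 3 if it prevents daily activity.

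**2. Is the pain anchor a study-wide choice?** Appendix 1 has 9 grading blocks: pain/itching, chills, nausea/vomiting, diarrhea, headache, fatigue, muscle pain, abdominal pain and joint pain. Six of them (nausea/vomiting, headache, fatigue, muscle, abdominal and joint pain) place prevented daily activity under Severe, as does Appendix 2. So it is not.

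**3. Recall.** In Table 10 the first in-office AE collection after the day 1 dosing visit is day 8 (±3). For a day 2 reaction the gap is 8 − 2 = 6 days, with a range of 3 to 9.

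**4. Effect on a count of three.** Let s be the share of affected records graded low and not corrected (assumed). With m true cases among 10 participants and no other Grade 3 event, P(count below 3) = P(Binomial(m, 1 − s) ≤ 2).

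| m | s = 0 | 0.10 | 0.25 | 0.50 |
|---|---|---|---|---|
| 3 | 0 | 0.271 | 0.578 | 0.875 |
| 4 | 0 | 0.052 | 0.262 | 0.688 |

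For m = 3 and s = 0.10: 1 − 0.9³ = 0.271.

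**5. Rule 7.8.2.1(a), cohort of 10.** Assume a local Grade 3 rate r = 0.20, a rate of other Grade 3+ events q = 0.10, and s = 0.25.
- Independent events: p = 1 − (1 − q)(1 − r(1 − s)). This goes from 0.280 to 0.235, and P(≥3 of 10) from 0.562 to 0.429.
- Every participant with another event also has a local one: p = q + (r − q)(1 − s). This goes from 0.200 to 0.175, and the probability from 0.322 to 0.248.
- Full overlap with r = q = 0.20: 0.322 at every s, so no loss.

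**6. Rule 7.8.2(2).** This rule names no cohort. For one event type at an assumed 20% rate, P(≥3 counted):

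| Participants | s = 0 | s = 0.25 |
|---|---|---|
| 10 | 0.322 | 0.180 |
| 20 | 0.794 | 0.595 |
| 30 | 0.956 | 0.849 |
| 60 | 0.9998 | 0.996 |

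The mean number vaccinated up to the third counted case rises from 3/0.20 = 15 to 3/0.15 = 20. At 10 participants, other assumed rates give 0.070 to 0.034 (10%) and 0.617 to 0.398 (30%).

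Steps 4 to 6 treat every local Grade 3 reaction as the affected kind. Any that involve a narcotic or exceed 10 cm would shrink the effect.

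**The case against.** The strongest reply is that the diary does not set the grade. It is a sample, Table 11 governs, and an investigator who applies Table 11 at the visit corrects any low entry. That stands, and it is why the loss could be zero. It does not close the gap for swelling and firmness, because the diary gives the investigator no functional entry to work from, only the participant's memory.

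For pain the reply is stronger. A reader might infer that the diary holds nothing on function, but it has daily ratings on activity-based anchors and medication names. A Moderate entry tells the investigator on which days function was affected and prompts the question. The wording is also open: pain that prevents daily activity goes beyond limiting it, and some participants would call it incapacitating and circle Severe.

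The swelling and firmness gap is narrower than it first appears. Table 11 grades the two in one row, so a swelling diameter covers size when both are present, and a painful swelling may show its functional effect under pain.

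Finally, oversight does not wait for a count. The SRC reviews every phase 1 cohort after its toxicity assessment period and each treatment-related toxicity within it (7.8.2, 7.8.2.1). A reaction graded one step low still reaches it.

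**Conclusion.** The mismatch is certain from the text; its consequence is possible but not shown. Some Grade 3 local reactions could be recorded low in a phase 1 primary endpoint and in the two Grade 3 counts. The documents do not allow the size to be estimated: every rate above is an assumption, and the 27% to 88% figures apply only to exactly three true cases with no other Grade 3 event.

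Three stronger readings are tempting and not supported:
- **The stopping rules would fail, or reactions would escape review.** The SRC sees related toxicities whatever the count. What is exposed is the reported severity and whether, or when, suspension is automatic.
- **Rule 2 loses nearly half its chance of triggering (0.322 to 0.180).** That holds only if the count is confined to one cohort of 10. Rule 2 has no such limit, so if cases accumulate the likelier effect is a later trigger.
- **The waking temperature on the treatment day precedes the dose, so fever that evening is missed.** Thermometers come from the study and diary training is on day 1, so a diary reading before the first dose would not normally exist. This is not part of the point.

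Cheap improvement; minor priority.

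**What to change.** In the Appendix 1 diary:
- Replace the pain anchors with Table 11's Grade 1 to 3 wording. Keep the present wording for itching, which Table 11 does not grade.
- Add one activity-interference item each for swelling and firmness: none, interferes, or prevents daily activity.
- Add a longest diameter for firmness. Rulers are already supplied (6.3.1).

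The cost is one changed grading block and a few more diary items for participants over 7 days. No visit, blood draw, endpoint or stopping rule changes.

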Fever (°C) ** (°F) **	38.0 – 38.4 100.4 – 101.1	38.5 – 38.9 101.2 – 102.0	39.0 – 40 102.1 – 104	> 40 > 104
Tachycardia - beats per minute	101 – 115	116 – 130	> 130	ER visit or hospitalization for arrhythmia
Bradycardia - beats per minute***	50 – 54	45 – 49	< 45	ER visit or hospitalization for arrhythmia
Hypertension (systolic) - mm Hg	141 – 150	151 – 155	> 155	ER visit or hospitalization for malignant hypertension
Hypertension (diastolic) - mm Hg	91 – 95	96 – 100	> 100	ER visit or hospitalization for malignant hypertension
Hypotension (systolic) – mm Hg	85 – 89	80 – 84	< 80	ER visit or hospitalization for hypotensive shock
Respiratory Rate – breaths per minute	17 – 20	21 – 25	> 25	Intubation

* Participant should be at rest for all vital sign measurements.

** Oral temperature; no recent hot or cold beverages or smoking.

*** When resting heart rate is between 60 – 100 beats per minute. Use clinical judgement when characterizing bradycardia among some healthy participant populations, for example, conditioned athletes.

Table 13: Clinical Abnormalities: Systemic

Systemic (General)	Mild (Grade 1)	Moderate (Grade 2)	Severe (Grade 3)	Potentially Life Threatening (Grade 4)
Nausea/vomiting	No interference with activity or 1 – 2 episodes/24 hours	Some interference with activity or > 2 episodes/24 hours	Prevents daily activity, requires outpatient IV hydration	ER visit or hospitalization for hypotensive shock
Diarrhea	2 – 3 loose stools or < 400 gms/24 hours	4 – 5 stools or 400 – 800 gms/24 hours	6 or more watery stools or > 800 gms/24 hours or requires outpatient IV hydration	ER visit or hospitalization
Headache	No interference with activity	Repeated use of non-narcotic pain reliever > 24 hours or some interference with activity	Significant; any use of narcotic pain reliever or prevents daily activity	ER visit or hospitalization
Fatigue	No interference with activity	Some interference with activity	Significant; prevents daily activity	ER visit or hospitalization
Myalgia	No interference with activity	Some interference with activity	Significant; prevents daily activity	ER visit or hospitalization
Systemic Illness	Mild (Grade 1)	(Moderate(Grade 2)	Severe (Grade 3)	Potentially Life Threatening (Grade 4)
Illness or clinical adverse event (as defined according to applicable regulations)	No interference with activity	Some interference with activity not requiring medical intervention	Prevents daily activity and requires medical intervention	ER visit or hospitalization

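### The sample solicited-event diary is not aligned with Table 11: its Severe injection-site pain sets a higher functional bar than Grade 3, and firmness and swelling entries are incomplete for grading

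*Combined protocol and SAP*

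**What the plan says.** **The grading scale.** Section 7.1 states "AEs will be graded according to the following tables", Section 7.4.1 repeats that the same guidance scale governs severity, and Section 8.3.2 reports solicited events by that grade. In Table 11, Grade 3 pain is "Any use of narcotic pain reliever or prevents daily activity". Grade 3 induration/swelling is "> 10 cm or prevents daily activity", and a footnote adds: "Induration/Swelling should be evaluated and graded using the functional scale as well as the actual measurement".

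**The diary.** Appendix 1 has one severity key for local events, for injection-site pain or itching. Moderate is "Interferes with activity, limiting activities of daily life" and Severe is "Severely limiting self-care activities of daily living, incapacitating". Item 2 (firmness) is Yes/No only. Item 3 (swelling) is Yes/No plus longest diameter. Neither asks about activity. Item 5 asks for the names of medications used for injection-site pain or itching.

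**Who grades.** Section 6.3.1 calls the diary a sample and says solicited events are captured at visits as well. Section 7.2 has the investigator record solicited events, and Section 7.4 has a qualified Investigator report severity.

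**The concern.** The diary is the only day-by-day record of the 7-day solicited period. If its terms do not match the grading table, or it omits an input that the table needs, the grade has to be rebuilt at a visit from the participant's memory, or it defaults to what the participant circled.

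Two uses depend on this. Incidence and severity of solicited local events is a phase 1 primary endpoint (Section 3.4.1.1) and a phase 2 secondary endpoint (Section 3.4.2.2.1). In phase 1, Grade 3 events also count towards two rules set at 3 or more participants: suspension of all vaccinations for the same or similar related Grade 3 event (Section 7.8.2), and suspension of enrollment into later cohorts for related events of Grade 3 or above (Section 7.8.2.1). Cohorts have 10 participants (Section 8.4), so one or two grades can decide whether a count is reached.

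**Working it through.** The plan states no figure to reproduce. The check sets the diary against Table 11.

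**1. Table 11 rows that match a solicited local event in Section 6.3.1**

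| Table 11 row | Needed for Grades 1 to 3 | What the diary supplies | Gap |
|---|---|---|---|
| Pain | Effect on activity; repeated non-narcotic use; any narcotic use | Mild/Moderate/Severe on its own key; medication names by day | Functional limb of Grade 3 |
| Erythema/redness | Diameter | Longest diameter | None |
| Induration/swelling | Diameter and effect on activity | Diameter for swelling only | Activity for both; diameter for firmness |

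Table 11 has 4 rows. Tenderness is not on the Section 6.3.1 list, which leaves 3. Only redness (1 of 3) can be fully graded from the diary.

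**2. Pain.** Table 11 Grade 3 is met by either of two limbs. The narcotic limb can be derived from item 5. The functional limb is the prevention of daily activity. Take pain that keeps someone from work or housework but not from washing or dressing. Table 11 makes it Grade 3. In the diary it meets "Interferes with activity, limiting activities of daily life" and does not clearly meet "Severely limiting self-care activities of daily living, incapacitating", so Moderate is a reasonable answer.

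**3. Comparison with the other diary keys.** Appendix 1 has 9 severity keys. Six concern an event with its own row in Table 11 or 13: injection-site pain, nausea/vomiting, diarrhea, headache, fatigue and muscle pain. Five of these repeat the Table 13 wording for Grades 1 to 3. For headache, Table 13 has "Significant; any use of narcotic pain reliever or prevents daily activity" and the diary has "Severe: Significant; any use of narcotic pain reliever or prevents daily activity". That leaves 6 − 5 = 1 that departs, injection-site pain, which is also the only local key.

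**4. Firmness and swelling.** In Table 11, Grade 1 requires both a size range and no interference with activity, while Grades 2 and 3 can be reached on size or on function. A diameter without a functional answer does not settle the grade. Because Table 11 has one combined row and swelling is measured, the missing firmness diameter matters mainly when firmness occurs without swelling or differs from it in extent.

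**5. Sensitivity of a 3-of-10 count (assumed rates only).** Let p be the true rate of related Grade 3 injection-site pain in a cohort and c the share recorded as Grade 3. Counting this event alone, and within one cohort of 10:

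P(X ≥ 3) = 1 − Σ (k = 0 to 2) C(10, k)(pc)^k (1 − pc)^(10−k)

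For p = 0.10 and c = 1: 1 − (0.3487 + 0.3874 + 0.1937) = 0.070.

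| Assumed p | c = 1 | c = 0.75 | c = 0.5 | c = 0.25 |
|---|---|---|---|---|
| 0.10 | 0.070 | 0.034 | 0.012 | 0.002 |
| 0.20 | 0.322 | 0.180 | 0.070 | 0.012 |
| 0.30 | 0.617 | 0.398 | 0.180 | 0.034 |
| 0.40 | 0.833 | 0.617 | 0.322 | 0.070 |

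Neither p nor c is in the documents. The table shows only that a small count is sensitive to mis-grading. It does not estimate how much occurs here.

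**The case against.** The strongest reply is that Appendix 1 is a sample form and not the grading instrument. The Investigator grades under Table 11, visits capture events too, and nothing makes the circled word the recorded grade. In phase 1 the day 8 visit falls nominally 8 − 7 = 1 day after the last diary entry, so recall is short. The word incapacitating in the Severe key is also loose enough that some participants whose pain stops daily activity would circle Severe. The Safety Review Committee (SRC) reviews treatment-related toxicity in the 7-day period with no grade threshold stated, and reviews each cohort, so an under-graded event would still be seen.

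All of this stands, and it limits the point to a risk. It does not remove it. No section tells staff to ask for firmness diameter or interference with activity, or how diary terms map to Table 11 grades. The CRF completion guidelines named in Section 7.4.3 are not among the documents. An event that the SRC sees below Grade 3 still does not count towards a Grade 3 rule.

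A reader might infer more than the documents support:

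- **That a 4 cm swelling which prevents daily activity would be graded 1 from the diary.** Grade 1 also requires no interference with activity, so the entry is incomplete and the Investigator has to ask.
- **That late diary collection in phase 2 experimental arm 3 makes the Grade 3 rules unreliable.** The diary after the second dose ends on day 35 and is collected on day 60 (25 days later), but a day 36 call is scheduled and the Grade 3 count rules are stated for phase 1 only. Section 7.8.3 states none for phase 2.
- **That itching is mis-keyed.** It shares the pain key but has no Table 11 row to conflict with, and Section 7.4.1 does not prescribe diary wording.

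**Conclusion.** The misalignment is in the text. The diary's pain key departs from Table 11 on the functional limb of Grade 3, and the firmness and swelling items do not collect everything that Table 11 requires. The consequence is a risk that Grade 3 local events are under-graded or graded from recall, in a phase 1 primary endpoint and in the phase 1 Grade 3 count rules. For pain the risk runs towards under-grading. For firmness and swelling the entries are incomplete, and no direction is shown.

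The size is unknown. The conclusion assumes that the diary used at sites resembles the sample and that no site instruction outside these documents already closes the gap. A claim that under-grading is established, or that Severe is stricter than Grade 3 in every case, would go too far: the narcotic limb is recoverable and the Investigator sets the grade.

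**What to change.** Reconcile Appendix 1 with Table 11, which the protocol already names as the scale, so no new clinical threshold is introduced:

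1. Use the Table 11 wording for Mild, Moderate and Severe injection-site pain.
2. Add a longest diameter in cm for firmness.
3. Add the Table 11 activity-interference question for firmness and for swelling.

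Grading by the Investigator under Table 11 stays as it is.

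The cost is one extra measurement and two short questions, only on days with firmness or swelling. Rulers are already provided (Section 6.3.1). The revised form would go to the IRB/IEC with a protocol amendment under Section 10.4.
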